8.1 EFFICACY ASSESSMENTS

Planned time points for all efficacy assessments are provided in the SoA ([Section 1.3](#)).

8.1.1 Nasal endoscopy: nasal polyp score

The NPS ([4](#), [5](#), [6](#)) is assessed by central video recordings of NE. The NPS is the sum of the right and left nostril scores, as evaluated by means of NE. Nasal polyp is graded based on polyp size described in [Table 3](#).

Table 3 - Endoscopic nasal polyp score

Polyp Score	Polyp Size
0	No polyps
1	Small polyps in the middle meatus not reaching below the inferior border of the middle turbinate
2	Polyps reaching below the lower border of the middle turbinate
3	Large polyps reaching the lower border of the inferior turbinate or polyps medial to the middle turbinate
4	Large polyps causing complete obstruction of the inferior nasal cavity

Nasal endoscopy should be performed at the end of the scheduled visits before the administration of IMP and should be preceded by local administration of anesthetic drugs in combination with a decongestant.

Standard video sequences will be downloaded or sent to a centralized reader. Centralized imaging data assessments and scoring by independent physician reviewer(s) for the imaging data will be performed for all endoscopies. To confirm eligibility at Visit 2, only the Visit 1 central reading will be made available to the site. In addition, at Visit 2, the Investigator will perform the NE to confirm the eligibility score and enter the result in the e-CRF. Thus, the participant will be considered eligible based on a Visit 1 central reading followed by a Visit 2 local reading NPS score of 5 or more and at least 2 on each side.

For the analysis of the primary endpoint, the central reading of Visit 2 will be used for comparison with the Week 24 reading. The sites will remove participant-identifying information from the imaging data header prior to sending the imaging data to the central reader.

Nasal endoscopy will be conducted at the Screening Visit (Visit 1), Visit 2, and Visits 4 to 9.

Further details on NE will be available in a separate operational manual provided to the sites.

8.1.2 Nasal congestion/obstruction symptom severity score

Nasal congestion/obstruction will be assessed by the participant using a diary on a daily basis from Visit 1 and throughout the study, on a 0 to 3 categorical scale (where 0 = no symptoms, 1 = mild symptoms, 2 = moderate symptoms and 3 = severe symptoms) (7):

Nasal congestion/obstruction will be scored as a reflective score (evaluation of symptom severity over the past 24 hours) by the participants (Table 4).

Table 4 - Nasal congestion/obstruction symptom severity score

Scale	Symptoms
0	No symptoms
1	Mild symptoms (symptoms clearly present, but minimal awareness and easily tolerated)
2	Moderate symptoms (definite awareness of symptoms that is bothersome but tolerable)
3	Severe symptoms (symptoms that are hard to tolerate, cause interference with activities or daily living)

The diary will be dispensed at Visit 1, and the diary will be checked by the study site at each visit.

A NC symptom severity score ≥ 2 at Visit 1 and a weekly average severity greater than 1 at the time of enrollment (Visit 2) are required and will be provided to the site to determine participant eligibility. The participant must have 4 or more measurements collected within 7 days prior to enrollment; the baseline will be the average of these measurements (E 24).

For the baseline to EOT/EOS analysis, the average of the symptom severity scores from the most recent 4 weeks before a scheduled visit will be used.

8.1.3 Computerized tomography scan: Lund Mackay score

The LMK system is based on localization with points given for degree of opacification: 0 = normal, 1 = partial opacification, 2 = total opacification. These points are then applied to the maxillary, anterior ethmoid, posterior ethmoid, sphenoid, and frontal sinus on each side. The osteomeatal complex (OC) is graded as 0 = not occluded or 2 = occluded. Adding the scores of these 6 parameters will derive a maximum score of 12 per side (left and right). The total score of the 2 sides will be used for analysis. This scoring system has been validated in several studies (8, 9, 10).

For participants in whom the OC is missing (because of a previous surgery), the reader should consider the location of the previous OC and provide a score (as if the OC were there).

Computerized tomography scan should be performed anytime during the Screening Period before the first administration of IMP and at Visits 7 and 9 (Weeks 24 and 52). Whenever possible, a cone beam CT scan should be utilized.

Details for CT will be available in a separate operational manual provided to the sites.

8.1.4 Nasal symptom diary: Disease specific daily symptom assessment and total symptom score

On a daily basis from Visit 1 and throughout the study, the participant will use a diary to:

- Respond to the morning individual rhinosinusitis symptom questions using a 0 to 3 categorical scale (where 0 = no symptoms, 1 = mild symptoms, 2 = moderate symptoms, and 3 = severe symptoms) (11):
 - Congestion and/or obstruction
 - Loss of sense of smell
 - Anterior rhinorrhea (runny nose)
 - Posterior rhinorrhea (postnasal drip)

The total symptom score (TSS) is a composite score (ranging between 0 and 9) consisting of the sum of the following symptoms assessed daily in the morning: nasal congestion/obstruction, decreased/loss of sense of smell, and rhinorrhea (average of anterior/posterior nasal discharge).

8.1.5 Visual analogue scale for rhinosinusitis

The visual analogue scale (VAS) for rhinosinusitis is used to evaluate the total severity (7). Rhinosinusitis disease can be divided into MILD, MODERATE, and SEVERE based on total severity VAS score (0 to 10 cm):

- MILD = VAS 0 to 3
- MODERATE = VAS >3 to 7
- SEVERE = VAS >7 to 10

The participant will be asked to indicate on a VAS the answer to the question below:

“How troublesome are your symptoms of your rhinosinusitis?”

The VAS ranges from 0 (Not troublesome) to 10 (Worst thinkable troublesome) (Appendix 10 [Section 10.10]).

8.2 SAFETY ASSESSMENTS

This section presents safety assessments other than AEs, which are presented in Section 8.3.

Planned time points for all safety assessments are provided in the SoA (Section 1.3).

8.2.1 Physical examinations

Physical examinations will include an assessment of general appearance, skin, eyes, ear/nose/throat, heart, chest, abdomen, reflexes, lymph nodes, spine, and extremities. All deviations from normal will be recorded, including those attributable to the participant’s disease.

Physical examinations will be performed at Visits 1, 7, and 9.

8.2.2 Vital signs

Vital signs including systolic and diastolic blood pressure (mmHg), pulse rate (beats per minute), respiratory rate (breaths per minute), and body temperature (forehead [temporal] temperature; degrees Celsius); and body weight (kg) will be measured at Visit 1, Visit 2, and Visits 5 to 9. Height (cm) will be measured at screening (Visit 1) only. Vital signs will be measured in the sitting position at each visit and will be measured prior to receiving IMP using preferably the same arm at each visit.

8.2.3 Electrocardiograms

A standard 12-lead electrocardiogram (ECG) will be performed at the sites at the Screening Visit (Visit 1). In case of an abnormal ECG finding, the Investigator should enter details into the e-CRF. At Visit 2, the Investigator should use his/her medical judgment to consider whether the participant is eligible for the study.

8.2.4 Clinical safety laboratory assessments

- See Appendix 2 (Section 10.2) for the list of clinical laboratory tests to be performed and the SoA (Section 1.3) for their timing and frequency.
- The Investigator must review the laboratory report and record any clinically significant changes occurring during the study as an AE. The laboratory reports must be filed with the source documents. Abnormal laboratory findings associated with the underlying disease are not considered clinically significant, unless judged by the Investigator to be more severe than expected for the participant’s condition.

- All laboratory tests with values that are considered clinically significantly abnormal during participation in the study should be repeated until the values return to normal or baseline or are no longer considered clinically significant by the Investigator.
 - If such values do not return to normal/baseline within a period of time judged reasonable by the Investigator, the etiology should be identified and the Sponsor notified.
 - All protocol-required laboratory tests, as defined in Appendix 2 ([Section 10.2](#)), must be conducted in accordance with the laboratory manual and the SoA ([Section 1.3](#)).
 - If laboratory values from non-protocol-specified laboratory tests performed at the institution's local laboratory require a change in participant management or are considered clinically significant by the Investigator (eg, SAE or AE or dose modification), then the results must be recorded in the e-CRF.

8.2.5 Pregnancy testing

A serum pregnancy test will be performed at Visit 1, and urine pregnancy tests will be performed at Visit 2 and q4w thereafter. A negative result must be obtained at both Visit 1 and Visit 2 prior to the first administration of IMP. A urinary test could be performed at home as part of visit with or without the assistance of a home care provider. In case of positive urinary test, the study intervention will be withheld and a serum pregnancy test to confirm the pregnancy should be performed as soon as possible. Pregnancy will lead to definitive treatment discontinuation in all cases.

- Refer to [Section 5.1](#) Inclusion Criteria for pregnancy testing entry criteria; the Investigator is responsible for the review of medical history, menstrual history, and recent sexual activity to decrease the risk for including a woman with an early undetected pregnancy.
- Additional serum or urine pregnancy tests may be performed, as determined necessary by the Investigator or required by local regulation, to establish the absence of pregnancy at any time during the participant's participation in the study.

8.2.6 Suicidal ideation and behavior risk monitoring

Not applicable.

8.2.7 Hypersensitivity monitoring

Allergic reaction is a potential risk associated with the administration of most therapeutic monoclonal antibody treatments.

Allergic reactions may be defined as allergic reaction-mediated signs and symptoms experienced by participants during or shortly after a pharmacologic or biologic agent is given. These reactions may present in a variety of ways, including dizziness, headache, anxiety, dyspnea, hypotension, tachycardia, pruritus, rash, urticaria/angioedema, flushing, nausea or vomiting, and joint pain with fever. Allergic reactions may begin within a few hours and persist up to 24 hours after dosing.

Refer to Appendix 12 ([Section 10.12](#)), which describes the clinical criteria for the diagnosis of anaphylaxis.

Participants should be monitored for at least 30 minutes after each study site IMP administration for any signs or symptoms of a hypersensitivity reaction. Any instance of allergic reaction should be reported as an AESI ([Section 8.3.6](#)). Any anaphylactic reactions or acute allergic reactions that require immediate treatment will be an AESI with immediate reporting (within 24 hours), and study medication must be permanently discontinued. Trained personnel and medications should be available to treat anaphylaxis or any severe allergic reaction if it occurs. Furthermore, the study participants will be advised, when the IMP is administered at home, to self-monitor for potential signs and symptoms that may suggest a hypersensitivity reaction for at least 30 minutes after administration.

Anaphylactic reactions or systemic allergic reactions that are related to IMP and require treatment must be reported as an AESI (within 24 hours; for further details, see AESI definition in [Section 8.3.6](#)), and study medication must be permanently discontinued.

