7.1.1 Permanent discontinuation

In rare instances, it may be necessary for a participant to permanently discontinue study intervention. If study intervention is permanently discontinued, the participant will remain in the study to be evaluated for the assessments planned for the EOT/EOS Visit, with the exception of the CT scan. See the SoA ([Section 1.3](#)) for data to be collected at the time of discontinuation of study intervention and follow-up and for any further evaluations that need to be completed.

Participants must be withdrawn from the study (ie, from any further IMP or study procedure) for the following reasons:

- At their own request or at the request of their LAR (an individual or judicial or other body authorized under applicable law to consent on behalf of a prospective participant to the participant's participation in the procedures involved in the research)
- If, in the Investigator's opinion, continuation in the study would be detrimental to the participant's well-being
- In case of surgery for NP
- At the specific request of the Sponsor
- In the event of a critical protocol deviation, at the request of the Investigator or the Sponsor
- In the event of an anaphylactic systemic allergic reaction that is related to IMP and that requires treatment
- In the event that the participant is diagnosed with a malignancy during the study, excluding carcinoma in situ of the cervix or squamous or basal cell
- Pregnancy
- Any opportunistic infection, such as TB or other infections whose nature or course may suggest an immunocompromised status (refer to Appendix 9 [[Section 10.9](#)])
- Met liver chemistry stopping criteria ([Section 7.1.2](#))

Handling of participants after permanent intervention discontinuation

Participants will be followed up according to the study procedures specified in this protocol up to the scheduled date of study completion or up to recovery or stabilization of any AE to be followed up as specified in this protocol, whichever comes last.

If possible, and after the permanent discontinuation of intervention, the participants will be assessed as soon as possible using the procedures normally planned for the EOT/EOS Visit (refer to SoA [[Section 1.3](#)]).

All cases of permanent intervention discontinuation must be recorded by the Investigator on the appropriate pages of the e-CRF when considered as confirmed.

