7.1.4 Rechallenge

Reinitiation of intervention with the IMP will be done under close and appropriate clinical and/or laboratory monitoring once the Investigator has considered, according to his/her best medical judgment, that the IMP was unlikely to have been responsible for the AE in question and that the selection criteria for the study are still met (refer to [Section 5](#)).

For a regional or national emergency declared by a governmental agency, contingency measures are included in Appendix 7: Contingency measures for a regional or national emergency that is declared by a governmental agency ([Section 10.7](#)).

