8.3.6 Adverse event of special interest

An AESI is an AE (serious or nonserious) of scientific and medical concern specific to the Sponsor's product or program, for which ongoing monitoring and immediate notification by the Investigator to the Sponsor are required. Such events may require further investigation in order to characterize and understand them. Adverse events of special interest may be added, modified, or removed during a study by protocol amendment.

For these AESIs, the Sponsor will be informed immediately (ie, within 24 hours), per the SAE notification described in [Section 10.3.4](#), even if it does not fulfill a seriousness criterion.

Adverse event of special interests for this study include the following:

- Anaphylactic or systemic allergic reactions that are related to IMP and that require treatment (refer to Appendix 12 [[Section 10.12](#)] for the definition of anaphylaxis)
 - Severe injection site reactions that last longer than 24 hours
 - Conjunctivitis, blepharitis, or keratitis
 - Serum sickness or serum sickness-like reaction
 - Clinically symptomatic eosinophilia (or eosinophilia associated with clinical symptoms)
 - Any infection meeting at least 1 of the following criteria:
 - Any SAE of serious infection
 - Requires parenteral (intravenous, intramuscular, SC) antimicrobial therapy
 - Requires oral antimicrobial therapy for longer than 2 weeks
 - Is a parasitic infection
 - Is an opportunistic infection (refer to Appendix 9 [[Section 10.9](#)])
- Note:** Antimicrobial therapy refers to antibiotic, antiviral, and antifungal agents.
- Significant elevation of alanine aminotransferase (ALT)
 - $ALT > 5 \times ULN$ in participants with baseline $ALT \leq 2 \times ULN$
 - or
 - $ALT > 8 \times ULN$ if baseline $ALT > 2 \times ULN$
 - Pregnancy of a female participant as well as pregnancy occurring in a female partner of a male participant entered in a study with IMP
 - Pregnancy occurring in a female participant entered in the clinical study or in a female partner of a male participant entered in the clinical study. It will be qualified as an SAE only if it fulfills one of the seriousness criteria (see Appendix 3 [[Section 10.3](#)]).
 - In the event of pregnancy in a female participant, IMP should be discontinued.
 - Follow-up of the pregnancy in a female participant or in a female partner of a male participant is mandatory until the outcome has been determined (See Appendix 4 [[Section 10.4](#)]).

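### Protocol 8.2.7, 7.1.1 and 8.3.6 give different triggers for the mandatory stop after an allergic reaction and for AESI reporting, so sites can act and report differently

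*Protocol*

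**What the plan says.** Protocol Section 8.2.7 contains two triggers for a permanent stop of study medication. The fourth paragraph names any anaphylactic reaction and adds that "acute allergic reactions that require immediate treatment will be an AESI with immediate reporting (within 24 hours), and study medication must be permanently discontinued"; causality is not mentioned. The last paragraph reads "Anaphylactic reactions or systemic allergic reactions that are related to IMP and require treatment must be reported as an AESI", again within 24 hours and again with a permanent stop.

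Section 7.1.1 has a list introduced by "Participants must be withdrawn from the study (ie, from any further IMP or study procedure) for the following reasons". The allergic-reaction bullet in that list is "In the event of an anaphylactic systemic allergic reaction that is related to IMP and that requires treatment".

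On reporting, the fourth paragraph of 8.2.7 also says "Any instance of allergic reaction should be reported as an AESI" and points to Section 8.3.6. The item there is "Anaphylactic or systemic allergic reactions that are related to IMP and that require treatment". Sections 8.3.1 and 8.3.6 require AESIs to reach the sponsor within 24 hours.

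Two further passages bear on the reading. Section 8.2.7 describes allergic reactions as arising "during or shortly after a pharmacologic or biologic agent is given". Section 7.1.4 allows dosing to restart once the investigator has considered that "the IMP was unlikely to have been responsible for the AE in question".

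**The concern.** A mandatory stop and a 24-hour reporting duty should each have one definition. Here the stop has three wordings, which differ on relatedness to IMP, on how urgently treatment is needed, and on the type of reaction. One of them also carries a different consequence. The AESI definition has two widths. No text says which wording prevails.

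Two outputs are exposed. The incidence of TEAEs leading to treatment discontinuation is a stated endpoint at 24 weeks (secondary) and at 52 weeks (exploratory). A TEAE is defined in Section 9.3.5.1 by when it occurs, not by cause, so an unrelated reaction that ends dosing counts. The other output is expedited AESI reporting, which depends on what a site takes an AESI to be.

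**Working it through.** The documents give no figure to reproduce. The check is to set the wordings side by side and run cases through them.

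**Conditions in each wording**

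| Wording | Reaction type | Related to IMP? | Treatment | Consequence |
|---|---|---|---|---|
| 8.2.7, fourth paragraph | anaphylactic, or acute allergic | not required | immediate | stop study medication |
| 8.2.7, last paragraph | anaphylactic, or systemic | required | required | stop study medication |
| 7.1.1 bullet | anaphylactic systemic (no conjunction between the two words) | required | required | end both IMP and study procedures |
| 8.2.7, AESI sentence | any allergic reaction | not required | not required | AESI |
| 8.3.6 item | anaphylactic, or systemic | required | required | AESI |

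**Cases**

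1. *Acute allergic reaction to an antibiotic (permitted as rescue in Section 6.8.1), treated at once, judged unrelated to IMP.* The fourth paragraph of 8.2.7 requires a permanent stop. The last paragraph and the 7.1.1 bullet do not cover it. It is an AESI under 8.2.7 and falls outside the 8.3.6 allergic-reaction item.
2. *Systemic, non-anaphylactic reaction, related to IMP, needing treatment but not immediately.* The fourth paragraph does not cover it, the last paragraph requires a stop, and the 7.1.1 bullet as worded does not list it. Both AESI wordings include it.
3. *Mild allergic reaction that needs no treatment.* No wording stops dosing. It is an AESI, hence a 24-hour report, under 8.2.7 but not under 8.3.6.
4. *Anaphylactic reaction, related, treated at once.* All three wordings stop dosing and both AESI wordings apply. The consequence still differs: 8.2.7 ends study medication, while the 7.1.1 list also ends study procedures. That list also conflicts with the other text of 7.1.1, which keeps participants in follow-up after permanent discontinuation.

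Cases 1 to 3 show that the wordings differ in which events they catch. Case 4 shows that they differ in consequence even where they catch the same event.

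**Size.** Planned enrolment is about 25 (Section 9.1). If all are dosed, one event classified differently changes the discontinuation incidence by 1/25 = 0.04, or 4 percentage points. This is a per-event figure. The documents give no rate of such reactions, so no expected number can be calculated.

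**The case against.** The strongest reply is that each sentence states a sufficient condition and none says that dosing stops only if its own conditions are met. A site applying the whole protocol would use the widest trigger and reach a single answer in case 1. This stands to the extent that the passages which do not cover case 1 do not direct continued dosing either, so divergence between sites is possible, not certain. It does not remove the problem. On that reading the relatedness condition has no effect for any acute reaction needing immediate treatment, and a site working from the discontinuation list in 7.1.1 would not be required to stop.

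A second reply is that context supplies relatedness, since the disputed sentence follows the instruction to observe participants after each injection at the site. But timing is not causality, which Section 10.3.3 makes a separate investigator assessment. The section's own description refers to agents in general, and its last paragraph adds the relatedness condition explicitly.

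Third, Section 8.3 says that the AESI definition is in 8.3.6, which favours that text. This is fair, but the wider sentence in 8.2.7 also cites 8.3.6, as if the two agreed. Similarly, the 7.1.1 bullet has probably just lost a conjunction; it is still the list that a site would consult.

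Two stronger readings are tempting. A reader might infer that an unrelated reaction would cost the primary analysis a responder. The documents do not support this. Stopping IMP is not a nonresponse trigger: Protocol 9.3.2 and SAP 4.3.2 name only NP surgery, systemic corticosteroids and missing Week 24 data. Sections 7.1, 7.1.1 and 7.2 aim to keep such participants in follow-up. If the reaction is treated with systemic corticosteroids, nonresponse follows whether or not dosing stops. A reader might also infer that the SAP's hypersensitivity counts depend on the wording a site follows. SAP Table 9 selects systemic hypersensitivity by a standard query plus corrective treatment, drug withdrawal or interruption, followed by medical review. Every event in dispute for the stop involves treatment, so it meets that part of the selector either way.

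Reactions to food, or NSAID reactions in participants with NERD, are poor illustrations. Section 8.2.7 ties allergic reactions to an administered agent, and Appendix 11 treats NERD separately from IgE-mediated allergy. Case 1 therefore uses an antibiotic.

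**Conclusion.** The inconsistency is real and lies within the protocol. There are three wordings of one mandatory stop, two definitions of the same AESI, and an unresolved question of whether the outcome is an IMP stop or study withdrawal. Sites can therefore act and report differently on the same event; the documents do not show that they will. The demonstrable reach is the incidence of TEAEs leading to treatment discontinuation, at 4 percentage points per event on the assumption that about 25 participants are dosed, together with 24-hour AESI reporting. The discontinuation endpoint is descriptive, since no hypothesis is tested. The correction is worth making because it concerns a mandatory safety action and an expedited report. This conclusion takes no position on which trigger is clinically right.

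**What to change.** Reconcile the two paragraphs of 8.2.7, the bullet in 7.1.1 and the item in 8.3.6 into one wording, repeated identically in each place. It should state:

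- whether relatedness to IMP is required;
- which reaction types are in scope, including systemic non-anaphylactic reactions and acute reactions that are not systemic;
- whether the consequence is a stop of IMP or withdrawal from the study.

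Align the sentence in 8.2.7 that makes every allergic reaction an AESI with 8.3.6. The sponsor's medical team decides the scope; no clinical rule is proposed here. The cost is one protocol wording change and a letter to sites, with no new procedure.
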